## 1) Protocol Title

Modulating Intraoperative Vasectomy Pain and Anxiety Using SmileyScope VR Interface

## 2) Objectives

The primary objective of this study is to assess the feasibility of using virtual reality goggles to modulate pre-operative anxiety and intraoperative pain during vasectomy. Feasibility will be measured via the following parameters:

Pain will be quantified in the following manner:

- Pre-operative, intra-operative, and post-operative physiological parameters (heart rate, temperature, oxygen saturation) measured by FitBit Versa 3 device
- Numeric pain scale pre- and post-vasectomy

Anxiety will be measured in the following manner:

- Pre- and post-vasectomy State-Trait Anxiety Inventory (STAI) anxiety score

Feasibility will be further measured via subjective post-procedure satisfaction surveys. Further discussion of data analysis is detailed in the Research Procedures and Data and Specimen Banking sections of this protocol.

The secondary goal of this study will be to evaluate the effectiveness of interactive virtual reality versus static virtual reality in reducing pain during the procedure. Secondary objectives will be assessed using the same outcome measures as primary objectives. This study will attempt to expand the use of SmileyScope virtual reality goggles, which have already been proven to reduce procedural pain in the pediatric population.

## 3) Background

Vasectomy is a safe and effective procedure for permanent sterilization in males. More than 500,000 vasectomies are performed annually in the United States, and that number is expected to grow rapidly in the coming years. The procedure is safe and can be quickly performed in an outpatient setting. Complications of vasectomy are rare, and can include hematoma and infection, spermatic granulomas, and post-vasectomy pain syndrome in rare cases. Like all outpatient surgical procedures where the patient is not under general anesthesia, vasectomies involve intraoperative and immediate post-operative pain. While use of the no-scalpel technique and local anesthetic reduces intraoperative pain, expected operative pain is still one of the main reasons patients cite for not undergoing the procedure.

In our current study, we aim to further modulate intraoperative pain using virtual reality goggles. In clinical trials, the SmileyScope device has been shown to reduce procedural pain in the pediatric population during venipuncture or intravenous cannulation. Results from those studies showed a statistically significant reduction in pain during intravenous procedures in the emergency department. This VR headset is undergoing study for approval by the U.S. Food and Drug Administration (FDA) to reduce pain and anxiety in patients aged 4 years and older undergoing needle blood draw or injection procedures. Currently, this device has been granted entrance to the FDA Safer Technologies Program. In this study, the SmileyScope virtual reality interface is

considered an investigational device because it is not yet approved for use in adult males undergoing vasectomy. We aim to use this same virtual reality modality to reduce pain during vasectomies.

## 4) Inclusion and Exclusion Criteria

Inclusion criteria:

1. Adult males  $\geq$  18 years old undergoing elective vasectomy

Exclusion criteria:

1. Have a serious comorbid illness or condition that, in the opinion of the investigator, may compromise the safety or compliance of the subject or preclude successful completion of the study
2. History of chronic pain disorder or chronic narcotic use
3. Significant refractive error, unilateral blindness, epilepsy, or other conditions such as skin infections, cancers etc., which could compromise the physical function of the headset

## 5) Procedures Involved

### Study Design

Patients will be randomized into one of three groups (interactive virtual reality, static virtual reality, and no virtual reality). Randomization sequence will be generated using a validated random number generator, and allocation concealment will be achieved via opaque envelope.

To ensure adequate power, the intended sample size has been calculated using the ANCOVA statistical test. Using G\*Power 3.1.9.4 software, a medium effect size 0.25, alpha 0.05, power 0.8, 3 groups and 1 covariate, the required sample size is 162 patients (54 patients per group, 1:1:1 ratio). No loss to follow up is anticipated.

All patients will be asked to wear the FitBit Versa 3 in the waiting room before the procedure. Patients randomized into one of the two virtual reality groups will be asked to wear the virtual reality goggles in the procedure room before the vasectomy. Before and after the procedure, a survey will be used to assess anxiety. Before the procedure, patients will also be asked to complete a pain scale survey to quantify baseline pain. After the procedure, patients will complete a pain scale survey to quantify their post-procedure pain. Physiologic data will be extracted from the FitBit device before, during, and after the vasectomy.

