## 6) Data and Specimen Banking

The following datapoints will be collected at initial clinic visit:

- Medical Record Number
- Age
- Date of Birth
- Sex
- Race/Ethnicity
- Marital Status
- Medical History
- Medications

The following data will be collected pre-procedure:

- Numerical anxiety scale survey (Modified 6-term STAI-S anxiety scale)
- Baseline pain measure
  - o “Please rate your current pain from 0 (no pain) to 10 (worst pain imaginable).”
- Physiologic data provided by FitBit Versa 3 – Data collected pre-procedure in waiting room. Data will be collected continuously during the time the patient is wearing the device. Data will be extracted from the FitBit after the procedure is finished and the patient has left.
  - o Heart Rate
  - o Oxygen saturation
  - o Skin temperature

The following data will be collected post-procedure:

- Length of procedure (start and end time)

- Numerical anxiety scale survey (Modified 6-term STAI-S anxiety scale)
- Numerical pain scale survey:
  - o Maximum pain felt during the procedure: "Please indicate the highest intensity of pain during the procedure on a scale of 0 (no pain) to 10 (worst pain imaginable)"
  - o Average pain felt during the procedure: "Please indicate the average intensity of pain during the procedure on a scale of 0 (no pain) to 10 (worst pain imaginable)"
- Post-procedure satisfaction:
  - o "How satisfied were you with today's procedure?"
  - o "If your urologist was using VR, would you be more or less likely to have the procedure?"
  - o "If your urologist was using VR, how likely would you be to recommend them to a friend undergoing the same procedure?"
  - o "How helpful was VR in managing your vasectomy today?"
  - o "Do you have any comments on today's procedure?"
    - Free text form for patient comments
  - o All questions will be answered via a 5-point Likert Scale as below:
    - 5 – Very Satisfied
    - 4 – Somewhat Satisfied
    - 3 – Neither Satisfied nor Dissatisfied
    - 2 – Somewhat Dissatisfied
    - 1 – Very Dissatisfied
    - 0 – Not applicable / Decline to Answer
- Physiologic data provided by FitBit Versa 3 - Data collected during the procedure and after the procedure in the waiting room
  - o Heart Rate
  - o Oxygen saturation
  - o Skin temperature

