## 9) Potential Benefits to Subjects

There may be reduction in vasectomy-associated pain for patients participating in this study, if they are randomized into one of the two VR headset groups. There may be no direct benefit if the patient is in the control group..

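### No masking is planned after assignment, so expectation and staff influence can affect the interactive-versus-static VR comparison; coded arms and divided tasks would reduce this cheaply

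*Combined protocol and SAP*

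**What the plan says.** Section 5 (Study Design) sets up three arms: "Patients will be randomized into one of three groups (interactive virtual reality, static virtual reality, and no virtual reality". Its only safeguards against bias are a random sequence and the statement that "allocation concealment will be achieved via opaque envelope". On wearing the headset ahead of surgery it adds: "Patients randomized into one of the two virtual reality groups will be asked to wear the virtual reality goggles in the procedure room before the" […]. Research Procedures, in the same section, gives both VR groups SmileyScope goggles.

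Section 2 names the comparison at issue, which concerns pain while the patient is operated on: "The secondary goal of this study will be to evaluate the effectiveness of interactive virtual reality versus static virtual reality in reducing pain during the" […]. On outcomes it says: "Secondary objectives will be assessed using the same outcome measures as primary objectives". Those are a numeric pain scale, the STAI anxiety score, satisfaction surveys, and "physiological parameters (heart rate, temperature, oxygen saturation) measured by FitBit Versa 3 device".

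Section 6 shows how pain during the procedure is rated. Afterwards the patient recalls his average and his maximum pain. The maximum is asked as "Please indicate the highest intensity of pain during the procedure on a scale of 0 (no pain) to 10 (worst pain imaginable". Anxiety and satisfaction are also questionnaire answers, and one item asks how helpful VR was.

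Section 11 has residents, students and fellows both collect and analyse the data. No section says whether patients, operator, survey staff or analysts are masked, who administers the surveys, or what the two VR programs contain.

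**The concern.** Concealment by envelope protects the act of assignment. It does nothing once the arm is known and the patient is asked to rate his pain.

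The static arm is what separates the effect of interactive content from the effect of wearing a headset. If a patient believes he received the lesser program, or staff who know the arm prompt differently, his ratings can move for reasons other than content. An interactive-static difference could then not be attributed cleanly to interactivity, which is the secondary question.

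Both arms use the same device, so the headset alone need not tell the person collecting the survey which program was shown. Some of this influence can be removed without new staff or patients, and the plan does not do so.

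**Working it through.** **The plan's own figure.** Inputs from section 5: f = 0.25, alpha 0.05, power 0.80, 3 groups, 1 covariate. For the ANCOVA F test, λ = f² × N, with 2 and N − 4 degrees of freedom.
- The smallest N reaching 80% power is 158: λ = 0.0625 × 158 = 9.875, power 0.802.
- At the stated 162: λ = 0.0625 × 162 = 10.125, power 0.813.

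The stated 162 (54 per group) is therefore reproduced to within 3%. Masking does not alter it, and no figure in the plan is disputed here.

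**What is and is not protected, from the text.**

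| Step | Where | Protection planned |
|---|---|---|
| Assignment | Section 5, Study Design | Random sequence, opaque envelope |
| Patient's pain, anxiety and satisfaction ratings | Section 6 | None stated |
| Handling of surveys | Sections 6 and 11 | None stated |
| Analysis | Sections 7 and 11 | None stated; the same staff collect and analyse |
| Device-recorded physiology | Sections 2, 5 and 6 | Not self-reported, but analysts not stated to be masked |

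**Illustration of scale.** The size of the bias is an assumption, because the documents give none. Take 54 versus 54 patients, an unadjusted two-sided t test at 0.05 with 54 + 54 − 2 = 106 degrees of freedom, no true difference, and a systematic shift of b SD in the ratings.
- Standard error of the difference in SD units: √(2/54) = 0.192.
- Noncentrality: b × √(54/2) = b × 5.196.
- The chance of p<0.05 comes from the noncentral t distribution.

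| Assumed bias b (SD) | Noncentrality | Chance of p<0.05 |
|---|---|---|
| 0 | 0 | 5% |
| 0.1 | 0.52 | 8% |
| 0.2 | 1.04 | 18% |
| 0.3 | 1.56 | 34% |
| 0.4 | 2.08 | 54% |
| 0.5 | 2.60 | 73% |

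**The case against.** The strongest reply is that little can be masked here and that part of the mechanism cannot be seen in the documents. Four points in it stand, and each limits what may be inferred.

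- **Patient masking.** A reader might infer that the VR comparison could be fully masked to patients. The documents do not support this. They do not describe either program, and a patient whose program responds to him may well notice. He can be kept unaware only of which program is expected to do better. Nor do they say whether the content can be seen or heard by others in the room, so masking of the operator cannot be assumed.
- **What patients are told.** A reader might infer that patients know their arm as interactive or static. Those labels stand in the protocol. The consent wording was not available for review and may already be neutral. Section 9 is even-handed between the VR arms: "There may be reduction in vasectomy-associated pain for patients participating in this study, if they are randomized into one of the two VR headset groups".
- **Outcomes.** A reader might infer that the comparison rests on self-report alone. Section 2 lists FitBit physiology among the pain measures. It gives only limited reassurance, since section 7 plans to report physiology through its correlation with pain scores and names no between-arm analysis of it.
- **Scope.** A reader might infer that this is the only comparison that can be protected. Analysts could be masked for all three arms. Survey staff who meet patients after headset removal could in principle be masked for no VR too, although the VR-helpfulness item could reveal the arm.

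It is also fair to say that the comparison is secondary to a feasibility objective. None of this removes the omission: the plan neither masks anyone nor declares the trial open-label.

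**Conclusion.** The point holds in limited form. Followed as written, the plan leaves expectation and staff influence uncontrolled in a stated secondary comparison whose main ratings come from patients, although partial protection is cheap. It is a low-severity improvement and does not invalidate the trial.

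The size of any bias cannot be derived from the documents. Under the assumed 0.2 to 0.4 SD, the false-positive rate would be about 18% to 54% instead of 5%. A reader might take the expected test statistic of 2.08 at 0.4 SD to mean that such a bias is by itself enough for significance. It is not: it gives p<0.05 in only about 54% of trials.

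The conclusion rests on two assumptions: that masking arrangements are not set out in material unavailable for review, and that people handling surveys can be kept from learning which program was shown.

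**What to change.** Amend section 5 (Study Design) as follows.
1. Code the two VR programs A and B in the envelopes, the case report form and the analysis dataset.
2. Keep those who hand out and collect the post-procedure surveys, and the analysts, unaware of the code. Divide tasks among the staff in section 11 so that whoever starts the program does not handle the surveys.
3. Check that patient-facing materials, in English and Spanish, describe the two VR programs neutrally, with neither presented as better. Describe this as masking to the hypothesis only.
4. State that VR versus no VR is open to patients and that its result includes expectation effects.

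If the sponsor declines, the protocol should at least say that the trial is open-label and that this limits the interactive-static comparison.

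**Cost.** A wording amendment with ethics approval and a division of tasks; no extra staff or patients. The downside is that masking stays partial: patients may guess, and the VR-helpfulness item or free-text comments may disclose the content to whoever reads them.

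### The sample size is for one three-group ANCOVA, but the protocol never names its outcome or covariate, and the only analyses it describes are correlations that do not compare the randomised arms

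*Combined protocol and SAP*

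**What the plan says.** All references are to the combined protocol and SAP.

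- **Section 5, Study Design.** The trial randomises 1:1:1 to interactive VR, static VR or no VR. The sample size is for an ANCOVA with "a medium effect size 0.25, alpha 0.05, power 0.8, 3 groups and 1 covariate, the required sample size is 162 patients", 54 per group. Neither the dependent variable nor the covariate is named. The same section says that before the procedure "patients will also be asked to complete a pain scale survey to quantify baseline pain" and that afterwards "patients will complete a pain scale survey to quantify their post-procedure pain". It does not link either score to the ANCOVA.
- **Section 2, Objectives.** The primary objective covers both anxiety and pain. "Feasibility will be measured via the following parameters" introduces the list: "Pre-operative, intra-operative, and post-operative physiological parameters (heart rate, temperature, oxygen saturation) measured by FitBit Versa 3 device", "Numeric pain scale pre- and post-vasectomy" and "Pre- and post-vasectomy State-Trait Anxiety Inventory (STAI) anxiety score". Satisfaction surveys are then added as a further measure of feasibility. Nothing is ranked. The secondary goal is to "evaluate the effectiveness of interactive virtual reality versus static virtual reality in reducing pain during the procedure", using the same outcome measures. For data analysis the reader is sent to Research Procedures and to Data and Specimen Banking.
- **Section 5, Research Procedures.** FitBit data are to be correlated with average or maximal pain during the procedure and with STAI-6. Pre-operative FitBit data are called a baseline, but not the ANCOVA covariate.
- **Section 6, Data and Specimen Banking.** Baseline pain, maximum pain during the procedure and average pain during the procedure are all collected on 0-10 scales. No analysis is given.
- **Section 7, Data Management.** Results are to be reported as the correlation between pain scores and FitBit data. ANCOVA is not mentioned.

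No section gives a multiplicity rule.

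**The concern.** An alpha of 0.05 and a power of 0.8 describe one test of one outcome. Here the form of the test is known (three groups, one covariate), but the outcome is not. Two things follow.

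First, the analysis that is written down does not use the randomisation. A correlation between pain and heart rate across all patients can be strong or weak whether or not VR reduces pain. A team that followed section 7 exactly would finish without an estimate of the VR effect.

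Second, when the group comparison is eventually made, the outcome and the covariate are open choices. The candidates are five measures, two versions of the pain score, and at least three possible covariates (baseline pain, pre-operative FitBit data, baseline STAI). If the choice is made after the data are seen, the 5% no longer describes the chance of a false claim.

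**Working it through.** **1. Reproduce the plan's figure.** Inputs from Study Design: f = 0.25, alpha 0.05, power 0.8, 3 groups, 1 covariate. Power of the group effect comes from the noncentral F distribution with df1 = 2, df2 = N - 3 - 1 and noncentrality N × f².

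- N = 158: noncentrality 158 × 0.0625 = 9.875, df2 = 154, power 0.802. This is the smallest N that reaches 0.80 (159 for equal groups).
- N = 162: noncentrality 162 × 0.0625 = 10.125, df2 = 158, power 0.813.

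The stated 162 is slightly above the minimum and is sound for one outcome. Using 0, 1 or 2 covariates does not change the minimum N.

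**2. Look for the outcome, the covariate and the group comparison.**

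| Section | Outcome for the ANCOVA | Covariate | Comparison of arms |
|---|---|---|---|
| 2 Objectives | five measures plus satisfaction, unranked | none | interactive v static named as a goal; no method |
| 5 Study Design | not named | one, not named | ANCOVA, for sizing only |
| 5 Research Procedures | average or maximal pain, for correlation | none | none |
| 6 Data and Specimen Banking | maximum and average pain both collected | none | none |
| 7 Data Management | pain scores, for correlation | none | none |

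Following the pointer in section 2 does not fill the gap.

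**3. What free choice of outcome could cost (illustration).** Suppose the three groups are compared at 0.05 on each measure, VR has no effect, and any significant result is claimed. With independent measures the chance of at least one false claim is 1 - 0.95⁵ = 0.226. For correlated measures, simulated F tests on equicorrelated normal outcomes (60,000 sets, df 2 and 158) give the values below. The documents give no correlations; those shown are assumed.

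| Five measures, pairwise correlation | 0 | 0.3 | 0.5 | 0.7 |
|---|---|---|---|---|
| Chance of a false claim | 0.226 | 0.211 | 0.188 | 0.152 |

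| Better of two pain scores, correlation | 0.5 | 0.7 | 0.8 | 0.9 |
|---|---|---|---|---|
| Chance of a false claim | 0.093 | 0.084 | 0.081 | 0.072 |

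**4. Does naming one outcome and baseline pain keep N = 162 valid?** Take f = 0.25 in unadjusted SD units and let r be the assumed correlation of baseline pain with the outcome. The effective effect size is 0.25 / √(1 - r²).

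- r = 0: 0.250, power 0.813
- r = 0.3: 0.25 / √0.91 = 0.262, power 0.850
- r = 0.5: 0.25 / √0.75 = 0.289, power 0.913

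Even a useless covariate leaves power at 81%. By contrast, keeping all five measures co-primary with Bonferroni (0.05 / 5 = 0.01 each) needs 227 patients, or 228 as 76 per group; 162 would then give about 60% power per outcome.

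**5. Side note on interactive v static (54 v 54).** With 158 df, 80% power needs a difference of about 0.54 covariate-adjusted SD. The 95% confidence interval half-width is 1.975 × √(2/54) = 1.975 × 0.1925 = 0.38 adjusted SD.

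**The case against.** The strongest reply is that this is a feasibility study with no written confirmatory claim, that the ANCOVA is identified, and that pain is the obvious outcome. Part of this stands. The test is identified, so it would be wrong to say that alpha and power belong to no test at all; what is missing is the outcome and the covariate. But feasibility is itself defined by the pain and anxiety measures, the trial is randomised and sized for adequate power at 0.05, and pain and anxiety stand side by side in the primary objective. Even if pain is accepted, maximum versus average remains open.

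Three stronger readings are tempting and are not supported:

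- A reader might infer that the trial's error rate is 15-23%. No section says that each measure will be tested at 0.05 or that any hit counts as success. Those figures show what the wording permits, not what it plans.
- A reader might infer that 0.8 power is claimed, and missed, for interactive versus static VR. Study Design makes no such claim, and a secondary comparison need not reach 80%.
- A reader might see a contradiction between post-procedure pain in Study Design and the during-procedure scores in section 6. This is better read as loose labelling of when the survey is completed.

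It is also fair to say that making pain the sole primary outcome changes the objective, and that baseline pain may be a weak covariate: chronic pain is an exclusion, so scores may cluster near zero (an inference; no data are given). Step 4 shows that a weak covariate does no harm to power.

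**Conclusion.** The point holds, and should be corrected before data are seen. The sample size is right for one three-group ANCOVA (81% power at f = 0.25), but the protocol does not attach it to an outcome or a covariate, and the analyses it does describe are correlations that cannot answer the randomised question. This is more than missing detail: applied literally, section 7 yields no VR effect, and the outcome that carries the 5% can be selected afterwards.

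The size of the selection problem is conditional. It is about 15-23% if five measures were each tested at 0.05 and any hit claimed (correlation 0.7 to 0), and about 7-9% if only the better of two pain scores were picked (correlation 0.9 to 0.5). Both rest on assumed correlations and normal outcomes. Five is a minimum count, since satisfaction and the second pain score add more.

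**What to change.** Amend these places together, before data are seen, with no change in N.

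1. **Section 5, Study Design.** State that alpha 0.05, power 0.8 and N = 162 apply to one intra-operative pain score (0-10), compared across the three groups by ANCOVA with baseline pain as the covariate. Maximum or average is equally acceptable, provided it is fixed now. Baseline pain is proposed because it is planned for every patient.
2. **Section 2, Objectives.** Name that score as the single primary efficacy outcome. Make the other pain score, STAI, heart rate, temperature, oxygen saturation, satisfaction and the interactive versus static comparison secondary, reported as estimates with 95% confidence intervals and no confirmatory claim. Two further sentences must be brought into line, or they will contradict the new text: the one that adds satisfaction as a further measure of feasibility, and the one that gives the secondary objectives the same outcome measures as the primary.
3. **Section 5, Research Procedures, and section 7.** State that the primary result is the three-group ANCOVA and that the correlations are descriptive. In Research Procedures, replace the either/or choice of pain score with the chosen primary score and the other as secondary.

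Optionally, note in Study Design that interactive versus static has 80% power only for about 0.54 covariate-adjusted SD, so a non-significant result would not show equivalence.

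The cost is protocol wording; no new data and no extra patients are needed. The real price is that anxiety and physiology lose primary status, and success cannot be claimed on whichever measure turns out positive.
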